**\*Basic metabolic panel (BMP) will be collected at baseline only.**

**Aim #3: Tertiary Outcomes.** The tertiary endpoints evaluate patient and clinician assessment of therapy. For the patient perception/satisfaction these include: (1) relief of symptoms, and (2) comfort/tolerance. For the clinician perceptions these include: (1) expected/perceived patient outcomes, (2) patient comfort & tolerance, and (3) ease of use.

These **endpoints** will establish comparability of HVNI to NIPPV in Acute Hypercapnic Respiratory Distress.

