**Vapotherm, Inc**  
**Hypercapnia Stabilization RCT NIPPV v HVNI**  
**Confidential**

## II. Overall Study Objective

The **overall objective** of this randomized study is to evaluate the efficacy of HVNI, in comparison to NIPPV, to clinically stabilize and provide respiratory therapy to patients who have COPD with moderate-to-severe hypercapnic respiratory distress upon presentation.

The **hypothesis**: HVNI is comparable to NIPPV in the stabilization and relief of moderate-to-severe hypercapnic respiratory distress upon presentation, by relieving the patient's dyspnea (breathlessness) within 4 hours to a comparable degree to NIPPV.

$$H_0: \mu_T \leq \mu_C - 1$$

$$H_a: \mu_T > \mu_C - 1,$$

where  $\mu_T$  and  $\mu_C$  are the improvement in modified BORG at 4 hours for treatment (Vapotherm) and control (NIPPV), respectively, and the non-inferiority margin is 1.

To test this hypothesis, the study will be conducted with the following specific aims:

**Aim #1: Primary Outcome.** The primary endpoint is to evaluate the patient's relief of dyspnea, as measured by the modified Borg, rated perceived dyspnea [RPD 0-10], during the 4-hour post-therapy initiation interval. These measurements will be compiled over the time course of the study – baseline, 30min, 1h, and 4h.

**Aim #2: Secondary Outcomes.** The secondary endpoints evaluate treatment failure (need for intubation), indices of Work of Breathing (patient vitals [HR, RR, SpO2]), patient's clinical stability during hypercapnic respiratory distress, as measured by an index of patient communication capability [Patient Stability Index: 0-10], venous blood gases (pH, PCO2, PO2, bicarbonate, base excess), basic metabolic panel\* (lactate, Na+, K+, Cl, glucose), and patient disposition (length of stay [LOS]). These measurements will be compiled over the time course of the study – baseline\*, 30min, 1h, and 4h. The Patient Stability Index is described in the protocol.

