### **Sample Size:**

This trial will randomize subjects 1:1 to Vapotherm:NIPPV. A total sample size of 64 subjects (~32 per arm) randomized with endpoint data, and a one-sided alpha of 0.025 will provide at least 80% power to demonstrate non-inferiority. This sample size assumes a difference of 0.9 between treatment and control with standard deviation of 2.4 and 2.9 for treatment and control, respectively, and a non-inferiority margin of 1.0.

Allowing for up to 20% attrition, approximately 80 subjects (40 per arm) will be enrolled in order to achieve 64 subjects with an endpoint.

From Doshi et al, comparable moderate-to-severe hypercapnic respiratory distress patient data was analyzed, which informed this sample size calculation's assumed difference and standard deviations in treatment (HVNI) and control (NIPPV) for the modified Borg score.

Change in modified Borg over 4 hours	Mean	Standard Deviation
NIPPV arm (Control)	-3.208	2.431
HVNI arm (Treatment)	-4.143	2.931

The minimal clinically important difference (MCID) for modified Borg was informed from literature, as a difference value of 1.0.

**NOTE:** As this is an Emergency Department or inpatient acute care study, and treatment is often immediate due to need for maintaining patient safety, there is an expected patient dropout (i.e. incomplete or unusable subject number) of randomized & enrolled patients into this study. After presenting to the ED or inpatient acute care setting, should the patients be transferred to another area of the hospital, the study procedures will continue until complete.

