### VI. Study Procedures

This head-to-head non-inferiority randomized control trial is non-blinded by necessity, as the devices are different in size, apparatus, and appearance, when viewed by both patients and clinicians. Patients may prefer HVNI over NIPPV or NIPPV over HVNI; however, this will not play a role in patient randomization. The study is a 1:1 randomized control design trial that will measure & compare the physiologic effect of the tested devices, specifically the effect on relieving patient dyspnea, and the stabilization and improvement of patient pH and PCO2 (venous blood gas). In addition, patient physiologic outcomes (e.g. HR, RR, BP, SpO2), patient disposition (LOS), patient venous blood gases (pH, PCO2, PO2, bicarbonate, base excess,) and patient & clinician assessment scores will be assessed and documented. Figure 1 illustrates a flowchart of overall study procedures. Except for the randomized study arm (HVNI or NIPPV device), the study procedures are identical.

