## VIII. Statistical Analysis

The data analysis will be “per protocol,” and per the “intention-to-treat” model. Baseline patient demographics and characteristics will be summarized, compared, and appropriate statistical testing will be performed for the continuous and categorical variables. Primary outcomes will be analyzed for statistical significance to test the null hypothesis. Assuming a non-normal data distribution for this randomized study design, the non-parametric Wilcoxon Signed Rank Sum test will be performed with significance interval of 0.05 on all applicable variables. Parametric analytical analogues (e.g. t-test) will be used if the measurements present a normal distribution. Otherwise, for the categorical variables, the Fisher’s Exact test will be performed and shown by category. Data for patient parameters will be compared across treatment arms and time-period using Repeated Measures analysis ANOVAs to assess dependence on treatment and interactions with time. Data will be compared and graphed accordingly for a visual comparison with accompanied statistical notations. Significance will be accepted where  $p < 0.05$ . Analyses will be performed using SAS version 9.2 or higher or comparable statistical software.

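### Section II lets the endpoints of all three aims establish comparability, but only the 4-hour Borg change has a margin; the others get difference tests that cannot show it

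*Combined protocol and SAP*

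**What the plan says.** Section II (Overall Study Objective) sets one formal hypothesis, on improvement in modified Borg at 4 hours, "and the non-inferiority margin is 1". It then lists three aims as the means of testing that hypothesis:

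- Aim 1 is Borg dyspnea.
- Aim 2 covers treatment failure (need for intubation), vital signs, the Patient Stability Index, venous blood gases, a baseline-only metabolic panel and length of stay.
- Aim 3 covers patient and clinician ratings.

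Directly after Aim 3 it states that these endpoints "will establish comparability of HVNI to NIPPV in Acute Hypercapnic Respiratory Distress". The sentence is not limited to the primary endpoint.

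The Sample Size text in Section V uses "a non-inferiority margin of 1.0", again for Borg only, and says of the planned number that "a one-sided alpha of 0.025 will provide at least 80% power to demonstrate non-inferiority".

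Section VIII (Statistical Analysis) covers the remaining variables with a Wilcoxon test or t-test at 0.05, repeated-measures ANOVA, and a categorical rule: "for the categorical variables, the Fisher’s Exact test will be performed and shown by category". Significance is accepted at p<0.05. The section gives no margin, equivalence test or confidence-interval rule for any secondary or tertiary endpoint. It does not say how a non-significant result on one of them will be interpreted.

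**The concern.** The conclusion announced in Section II and the methods in Section VIII do not fit together. A difference test can show that two arms differ. Failing to reject gives no bound on how far apart they may be, and so does not show that they are alike. For the Borg endpoint the margin solves this. For intubation, pH, PCO2 and the rest nothing does, so the only result under the listed methods that could be offered as comparability is a p-value of 0.05 or more.

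This matters most for Aim 2. The Background credits NIPPV with a 65% lower risk of intubation and a 46% lower risk of death, against usual care, in COPD exacerbation with hypercapnic failure. A statement that HVNI is comparable on intubation or gas exchange would carry clinical weight. In a trial sized for a Borg difference, it could rest on little more than low power.

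**Working it through.** **Inputs from the protocol.** The Sample Size text gives "A total sample size of 64 subjects (~32 per arm) randomized with endpoint data". It "assumes a difference of 0.9 between treatment and control with standard deviation of 2.4 and 2.9 for treatment and control, respectively", with margin 1.0, one-sided alpha 0.025, 80% power, 1:1 allocation, and about 80 enrolled (40 per arm) after a 20% allowance for attrition. The accompanying table shows that the 0.9 favours HVNI (−4.143 v −3.208).

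**Step 1: the plan's own figure.**
- Average variance = (2.4² + 2.9²)/2 = 7.085, so SD = 2.662. (The table attaches the two SDs to the opposite arms from the text. At 1:1 this does not change the result.)
- n per arm = 2 × 7.085 × (1.960 + 0.842)² / (1.0 + 0.9)² = 30.8, rounded up to 31, or 62 in total against the stated 64.
- At 32 per arm the standardised effect is 1.9 / (2.662 × √(2/32)) = 2.855. Power is 80.3% (noncentral t) or 81.5% (normal).
- 64 / 0.80 = 80 enrolled.

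The primary sample size reproduces and is not at issue.

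**Step 2: continuous secondary and tertiary endpoints, 32 per arm.** The calculation uses the two-sided t-test at 0.05, with noncentrality d / √(2/32) = 4d for a true difference of d SD.
- d = 0.3: non-significant in 78% of trials.
- d = 0.5: non-significant in 50%.
- 80% power is reached only at d = 0.71.
- Half-width of the 95% confidence interval = 2.00 × √(2/32) = 0.50 SD.

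The plan's own Borg figures give a direct illustration. Suppose HVNI were truly worse by the full margin of 1.0. The noncentrality is 1.0 / (2.662 × 0.25) = 1.50, power is 32%, and a difference test would be non-significant in 68% of trials. So the kind of test applied to the secondary endpoints would usually fail to flag a deficit equal to the limit set for the primary.

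**Step 3: treatment failure or intubation.** The documents give no rate, so the rates below are assumptions. Entries are the probability that the two-sided Fisher's exact test gives p≥0.05, by enumeration of all outcomes under two binomials.

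| Assumed rates, NIPPV v HVNI | 32 per arm | 40 per arm |
|---|---|---|
| 5% v 10% | 98% | 96% |
| 5% v 15% | 89% | 82% |
| 10% v 20% | 89% | 84% |
| 10% v 25% | 76% | 67% |
| 10% v 30% | 59% | 47% |

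The 40-per-arm column applies if everyone enrolled contributes an intubation outcome. At 32 per arm, with no events in one arm, the other needs 6 before the test is significant (p = 0.024).

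**Step 4: what margins on these endpoints would require.** The margins here are illustrative, with no true difference, one-sided alpha 0.025 and 80% power.
- Continuous, n per arm = 2 × (1.960 + 0.842)² / m²: 175 for m = 0.3 SD and 63 for m = 0.5 SD.
- Binary with a 10% rate in both arms, n per arm = 2 × 0.10 × 0.90 × (1.960 + 0.842)² / m²: 142 for a 10-point margin and 566 for a 5-point margin.

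All four exceed the 40 per arm to be enrolled.

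**The case against.** The strongest reply is that the confirmatory claim is already defined. Section II has one null hypothesis and one margin, about dyspnea within 4 hours. The sample size serves that hypothesis alone, Section VII names one primary parameter, and the other aims are labelled secondary and tertiary. On this view the comparability sentence loosely summarises a package led by the primary endpoint. That reading is possible. But nothing in the sentence says so, it follows the tertiary aim, and all three aims are introduced as ways of testing the hypothesis. The ambiguity is enough to need correcting.

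Four further points limit the concern.

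- A reader might infer that the plan equates p≥0.05 with comparability. It does not say this. Section VIII states when significance is accepted and is silent on the rest.
- A reader might add that many unadjusted tests invite chance claims of superiority. The documents claim superiority on no secondary endpoint, and leaving secondary endpoints unadjusted beside a single primary is common, so that charge is not supported.
- Section VI says the trial compares the devices, "specifically the effect on relieving patient dyspnea, and the stabilization and improvement of patient pH" and PCO2. That describes what is measured and makes no comparability claim.
- Thirty-two per arm is the number with Borg data. An intention-to-treat analysis is planned and intubation is recorded separately, so up to 40 per arm may be available, though post-randomisation exclusions are allowed. This is why both columns are shown. The larger number helps, but not enough to change the conclusion.

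**Conclusion.** The concern holds as a mismatch between the stated conclusion and the stated methods for the secondary and tertiary endpoints. It does not touch the primary test or its sample size. Nor do the documents show that the sponsor intends to read non-significance as comparability. They leave that route open, and no other listed method leads from these endpoints to the sentence.

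The size depends on assumed failure rates. Across the pairs examined, a two- to three-fold higher rate would be non-significant in 59% to 98% of trials at 32 per arm and 47% to 96% at 40 per arm. The continuous results need no assumed rate. They are in SD units for a t-test at 32 per arm, and differences smaller than about 0.7 SD are detected with less than 80% power. A non-significant result at this size is therefore weak evidence of comparability. The point is worth fixing before analysis because it changes what the trial may conclude on intubation and gas exchange.

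**What to change.** In Section II, reword the sentence after Aim 3 so that the comparability (non-inferiority) conclusion rests on the 4-hour Borg endpoint alone.

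In Section VIII, state that each secondary and tertiary endpoint compared between arms will be reported as a between-arm estimate with a 95% confidence interval, labelled supportive. Add that p≥0.05 on any of them will not be described as comparable or equivalent.

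The change needs no extra patients or data and leaves the primary analysis as it is. The cost is that the sponsor gives up comparability claims on endpoints that the design cannot support. Setting margins for chosen secondary endpoints instead would keep such claims possible, but at the illustrative margins above it would require a larger trial.

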# Vapotherm, Inc

## Hypercapnia Stabilization RCT NIPPV v HVNI

Confidential

### III. Subject Selection

Patients will be identified and recruited by study investigators or research staff trained on this particular trial. The study will initiate in an Emergency Department setting, or from an inpatient setting, and transfer to an acute-care unit that is sufficiently staffed and skilled in NIPPV and HVNI to support patients presenting with moderate to severe hypercapnic respiratory acidosis. Testing during this study will be performed in the presence of health care individuals who will provide appropriate supervision and staff training to maintain patient safety. The test will evaluate the patient's relief of dyspnea, clinical stability, WOB indices (vitals, RPD, ventilation, oxygenation), patient disposition, and patient and physician perceptions for each study arm before and during therapy for hypercapnic respiratory distress. Initial patient contact will be made by study investigators or research staff trained on this particular trial. Participants may or may not decide to enroll after being consented. Consent in this ED/acute-care-setting-based study will be obtained by a verbal consent prior to participation/randomization followed by written consent (when patient is medically stable), or a written consent prior to participation/randomization. The verbal consent will be obtained and documented in the patient chart along with a witnessed attestation. The written consent will be obtained once patient is able to participate in a consent discussion, when their respiratory symptoms are manageable.

#### **Inclusion Criteria – *Selection of Inclusion***

1. Adults, 18 years or older with a known or suspected diagnosis of COPD
  - a. Suspected diagnosis of COPD defined as a history of smoking or significant second-hand smoke, plus clinical history of wheezing, chronic cough, bronchospasm, or exacerbations, and/or exposure with hypercapnia
2. Presentation with acute hypercapnic respiratory failure defined as:
  - a. Moderate to Severe patient baseline hypercarbia/hypercapnia, defined as a baseline PCO2 of 60 mmHg or higher (as measured by venous blood gas)
3. Venous pH of 7.0 – 7.35

#### **Exclusion Criteria**

1. Severe metabolic derangements, e.g. suspected drug overdose, mixed acid/base disorder (bicarbonate at normal or above to be eligible)
2. Need for airway protection, e.g. neurologic disorder(s)
3. Primary condition of Congestive Heart Failure, e.g. Acute Severe Decompensated Heart Failure
4. Need for emergent intubation
5. Pneumonia diagnosis with significant infiltrate on chest x-ray that is clinically correlated with pneumonia
6. Inability to provide informed consent
7. Pregnancy
8. Known contraindication to perform procedures listed, or therapies described in the protocol
9. Respiratory arrest or significant respiratory depression on presentation
10. Significant nasal occlusion either unilateral or bilateral
11. Absence of spontaneous respiration or known contraindication to HVNI
12. Extreme agitation or uncooperativeness that would hinder either arm of randomized therapy
13. Determined by the clinician to be sufficiently unstable or unsuitable for this study

**Vapotherm, Inc**  
**Hypercapnia Stabilization RCT NIPPV v HVNI**  
**Confidential**

#### **IV. Study Design**

This will be performed as a prospective, unblinded (by definition), multicenter, 1:1 randomized non-inferiority design clinical trial to evaluate the efficacy of HVNI compared to NIPPV (two approved interventions for the management of acute respiratory distress) in the clinical stabilization and relief of moderate-to-severe respiratory distress requiring ventilatory support upon presentation. Patients deemed to fit the criteria for inclusion will perform the study procedures for one of the study arms of the randomized study design. Patient completion of either of the study arms will provide an evaluation of the efficacy of HVNI or NIPPV in stabilization and relief of respiratory acidosis and will record patient ventilatory/WOB indices, treatment failure, disposition, and physiologic parameters during a 4-hour therapy-response window. Additionally, tertiary outcomes will provide an evaluation of patient comfort, and therapeutic response, per the study aims. Patients are expected to complete the study in one session, per the noted parameter sampling intervals (baseline, 30min, 1hr, 4hr). After the patient completes the randomized study arm (HVNI or NIPPV), the clinicians and patients will complete perception score assessments. The clinical management will otherwise remain unchanged, based on individual study site standard of care and practice.

This study will utilize two arms. Patients presenting with acute hypercapnic respiratory failure (per Inclusion criteria, in need of clinical stabilization and relief of moderate-to-severe respiratory distress) who are escalated to treatment with a non-invasive respiratory support modality will be randomized to one of the following:

- Vapotherm high flow nasal cannula therapy (HVNI) administered as defined below (HVNI arm)
- Non-invasive positive pressure ventilation (NIPPV) delivered via single-limb circuit with a full face mask using a pressure support mechanical ventilator system (e.g., Resironics Vision, V60) administered as defined below (NIPPV arm)

The study design will focus on six distinct phases for each study arm, which will be identical except for the therapy randomization (HVNI or NIPPV): (1) Study Start, (2) Baseline Characterization, (3) Therapy Evaluation Interval 1, (4) Therapy Evaluation Interval 2, (5) Therapy Evaluation Interval 3, and (6) Study End. Primary, secondary, and tertiary outcomes will be completed upon the completion of all study phases.

The Study Start Phase will follow screening and consent, and will confirm randomization to either study arm, and gather the patient background, history, health, demographics, and current respiratory therapies. For Phase 2, Baseline Characterization will provide the initial clinical evaluation along with the baseline physiologic parameters, ventilation parameters, Patient Stability Index, and blood gases. For Phase 3, the Therapy Interval 1 will provide the current patient status at 30minutes post randomized therapy interval and will include this interval's physiologic parameters, ventilation parameters, Patient Stability Index, and venous blood gases. For Phase 4, the Therapy Interval 2 will provide the current patient status at 1hour post randomized therapy interval and will include this interval's physiologic parameters, ventilation parameters, Patient Stability Index, and venous blood gases. For Phase 5, the Therapy Interval 3 will provide the current patient status at 4-hour post randomized therapy interval and will include this interval's physiologic parameters, ventilation parameters, Patient Stability Index, and venous blood gases. Following the 3rd Therapy Evaluation Interval at 4hours, Phase 6 will be implemented, which concludes with Study End. Phase 6 will include Visual Analog Scale (VAS) for both patient and clinician assessment scores. The clinician and the patient will complete VAS perception scores for their randomized study arm (HVNI or NIPPV) at designated intervals.

**Vapotherm, Inc**  
**Hypercapnia Stabilization RCT NIPPV v HVNI**  
**Confidential**

This study will be conducted in an Emergency Department or Inpatient Critical Care setting, if applicable, where patient care and testing can be performed with appropriate supervision and staff training to maintain patient safety. In this acute-care setting study, participants may or may not decide to enroll after being consented. Patients may be excluded after randomization, as this study takes place in the ED or inpatient critical care unit and patients may need to be randomized and treated immediately to maintain patient safety. All respiratory interventions will be tracked during the study window for each patient.

**Vapotherm, Inc**  
**Hypercapnia Stabilization RCT NIPPV v HVNI**  
**Confidential**

## **V. Subject Enrollment**

Subjects will be solicited by investigators and consented as described above (Section III), due to the emergent need for treatment at time of initial presentation. Should subjects provide initial verbal or written consent, only then will data be compiled and used as part of the subject participation in this study (Aims 1-3). Once enrolled, and randomized 1:1 to study arms, the participants and investigators will complete data collection in all Aims during the course of the trial timeline.

